### 7.3.10 Duration of Complete Response

Duration of CR (in number of days) will be calculated from the first time a CR is observed to time of relapse (defined as the earliest time point whereby BM assessment or PB assessment indicate relapse/disease progression due to reappearance of leukemic blasts in PB or  $\geq 5\%$  leukemic blasts in BM; see Section 7.3.6). The duration of CR will be censored at the last available time point at which a relapse/disease progression was not observed. Duration of CR will be estimated using a Kaplan-Meier method for subjects who achieved a CR during the study.

The median and quartiles of duration of complete response, as well as their respective 95% CIs will be provided.

To take all subjects in the Efficacy Analysis Set into consideration when analyzing duration of CR, a separate Kaplan-Meier analysis including all subjects will be conducted with a 0-day event duration assigned to subjects who did not achieve a CR. The median and quartiles of duration of complete response, as well as their respective 95% CIs will be provided.

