4.2 Discussion of Study Design

This trial compares SGI-110 and TC for treatment of subjects with AML who are not considered candidates for intensive remission induction chemotherapy at the time of enrollment. While the 7+3 intensive chemotherapy for remission induction with potential for hematopoietic cell transplant (HCT) has been an established standard of care for decades in patients who are fit to receive this intensive treatment, there is no standard of care or universally approved therapies for treatment of AML patients who are not candidates for standard intensive remission induction chemotherapy. For these patients, goals of therapy are to prolong and improve quality of life by inducing complete remission for as long as possible, as well as to avoid treatment-induced early mortality.

Eligibility for this trial is based on precedented criteria of unsuitability for intensive remission induction chemotherapy (Ferrara et al 2013; Kantarjian et al 2006; Kantarjian et al 2010) and other randomized trials in a similar patient population (Burnett et al 2007; Kantarjian, Thomas et al 2012; Dombret et al 2014). The co-primary endpoints for this trial are CR rate and OS.

FDA has accepted durable CR in hematological malignancies as an established surrogate for clinical benefit because patients who achieve durable CR have been shown to survive longer than those who do not (Appelbaum et al 2007). Numerous studies have demonstrated that subjects achieving CR survive longer than subjects not achieving CR (Sievers et al 2001; Larson et al 2005; de Greef et al 2005; Kantarjian et al 2003). FDA has also granted regular approval for treatment of hematologic malignancies on the basis of durable CR. In these settings, durable CRs were considered an established surrogate for a better life and possibly a longer life (Johnson et al 2003).

The trial includes a co-primary endpoint of OS to confirm no decrement in survival from severe toxicity. Secondary endpoints include CRc (CR+CRi+CRp) rate, NDAOH, PFS, number of transfusions, health-related QOL, duration of CR, and safety.

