11.6.10 Duration of CR

Duration of CR (in number of days) will be calculated from the first time a CR is observed to time of relapse (defined as the earliest time point whereby BM assessment or PB assessment [see Section 11.6.6] indicate relapse/disease progression due to reappearance of leukemic blasts in PB or $\geq 5\%$ leukemic blasts in BM). The duration of CR will be censored at the last available time point at which a relapse/disease progression was not observed. Duration of CR will be estimated using the Kaplan-Meier method for subjects who achieved a CR during the study. To take the proportion of responders into consideration when analyzing duration of CR, a separate analysis including all subjects will be conducted with a 0-day event duration assigned to subjects who did not achieve a CR, with the 2 groups compared using a log-rank test.

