### 3.2.2 Secondary Endpoints

- CRc (CR+CRi+CRp) rate.
- NDAOH.
- PFS, defined as the number of days from date of randomization to date of disease progression, initiation of an alternative anti-leukemia therapy, or death, whichever occurs first.
- Number of red blood cell (RBC) or platelet transfusions (units) over the duration of the study treatment.
- Health-related QOL by EQ-5D (consisting of the EQ-5D-5L descriptive system and the EQ Visual Analogue Scale [EQ VAS]).
- Duration of CR, defined as the time from first CR to time of relapse.
- Incidence and severity of adverse events (AEs).
- 30- and 60-day all-cause mortality.

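### Duration of CR censors subjects who die in remission, so Kaplan-Meier overstates how long responders stay alive in CR and this endpoint cannot show a difference between arms in deaths in remission

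*SAP*

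**What the plan says.** The SAP's endpoint list (3.2.2) gives: "Duration of CR, defined as the time from first CR to time of relapse". Section 7.3.10 repeats this ("Duration of CR (in number of days) will be calculated from the first time a CR is observed to time of relapse") and limits relapse to marrow or blood assessments that "indicate relapse/disease progression due to reappearance of leukemic blasts in PB" or show at least 5% leukemic blasts in the marrow. The censoring rule is "The duration of CR will be censored at the last available time point at which a relapse/disease progression was not observed". The estimator is standard: "Duration of CR will be estimated using a Kaplan-Meier method for subjects who achieved a CR during the study".

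A second analysis covers the whole Efficacy Analysis Set: "a separate Kaplan-Meier analysis including all subjects will be conducted with a 0-day event duration assigned to subjects who did not achieve a CR". Protocol 11.6.10 has the same event, the same censoring rule and the same all-subject analysis, there "with the 2 groups compared using a log-rank test". The SAP version gives medians and quartiles only.

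Neither document names death in CR as an event for this endpoint. Neither plans a cumulative incidence of relapse, a version with death as an event, or a count of deaths in CR by arm. PFS (SAP 7.3.6) does count death.

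**The concern.** Censoring is harmless when the censored subject could still have the event later and is no different in prognosis from those who stay under observation. A subject who has died in CR cannot relapse, so death is a competing event. With such deaths censored, Kaplan-Meier describes relapse in a setting where nobody in remission dies. A reader will take the reported median as the time responders spend alive and in remission, which is a shorter time.

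This matters because Protocol 4.2 justifies CR as an endpoint by pointing to durable CR, and duration of CR is the planned endpoint that measures durability. If one arm had more deaths in remission, its reported duration of CR would look no worse for it.

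**Working it through.** **1. Inputs from the documents.** CR rates of 0.20 (TC) and 0.30 (guadecitabine), 400 per arm, two-sided alpha 0.04 (SAP 4.0). The documents give no figure for duration of CR, time to relapse, or death in remission.

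**2. Reproducing the plan's own figure.** For the CR comparison:
- standard error under the null = √(2 × 0.25 × 0.75/400) = 0.0306
- standard error under the alternative = √((0.20 × 0.80 + 0.30 × 0.70)/400) = 0.0304
- power = Φ((0.10 − 2.054 × 0.0306)/0.0304) = 0.889, against about 89% stated.

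The figure reproduces. Expected responders are 0.20 × 400 = 80 and 0.30 × 400 = 120.

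**3. Effect of the rule.** Let λr be the hazard of relapse from CR and λd the hazard of death in CR without relapse, both constant.
- Kaplan-Meier with deaths censored targets exp(−λr t), with median ln 2/λr.
- The proportion alive and in CR is exp(−(λr + λd)t), with median ln 2/(λr + λd).
- The share of remissions ending in death is s = λd/(λr + λd).
- The ratio of the medians is (λr + λd)/λr = 1/(1 − s), whatever the relapse median.

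The second curve can never lie above the first, so the direction does not depend on the assumed values. The calculation censors at death; the plan censors at the last relapse-free time point, at or before death.

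**4. Numbers.** The shares and relapse medians (6, 8, 12 months) are assumptions. The planned analysis would report the relapse median itself, in every row.

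| Share ending in death (assumed) | Inflation of median | True median, relapse median 6 | True median, relapse median 8 | True median, relapse median 12 | Alive in CR at 12 months, relapse median 8 |
|---|---|---|---|---|---|
| 0% | 1.00 | 6.0 | 8.0 | 12.0 | 35.4% |
| 5% | 1.05 | 5.7 | 7.6 | 11.4 | 33.5% |
| 10% | 1.11 | 5.4 | 7.2 | 10.8 | 31.5% |
| 20% | 1.25 | 4.8 | 6.4 | 9.6 | 27.3% |
| 30% | 1.43 | 4.2 | 5.6 | 8.4 | 22.6% |
| 40% | 1.67 | 3.6 | 4.8 | 7.2 | 17.7% |

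For the 8-month column the planned 12-month estimate is 35.4% in every row.

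**5. Unequal arms.** Simulation with an 8-month relapse median in both arms, 120 guadecitabine and 80 TC responders, administrative censoring uniform over 9 to 30 months, 3,000 runs:

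| Assumed shares (guadecitabine, TC) | Planned medians, months | Medians with death as event, months |
|---|---|---|
| 30%, 10% | 8.1, 8.0 | 5.7, 7.1 |
| 10%, 30% | 8.0, 8.0 | 7.3, 5.5 |

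The planned medians are the same whichever arm has the excess. In the first row an average of about 32 guadecitabine and 7 TC responders die in CR.

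**6. The all-subject version.** At the planned CR rates, 400 − 80 = 320 TC subjects (80%) and 400 − 120 = 280 guadecitabine subjects (70%) have a 0-day event, so the median is 0 days in both arms however deaths in CR are handled. In the TC arm the curve starts at 0.20 and all three quartiles are 0. In the guadecitabine arm only the 75th percentile is above 0, reached when the responder curve falls to 0.25/0.30 = 0.83, and that curve still censors deaths in CR. This analysis does not repair the problem.

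**The case against.** **The text is not wholly explicit.** SAP 7.3.10 refers to 7.3.6 for relapse/progression, and death is the third item in the 7.3.6 progression list; Protocol 11.6.10 points likewise to 11.6.6. A programmer could follow the pointer and count death. But 7.3.10 ties the event to reappearing blasts on a marrow or blood assessment, and the endpoint lists in both documents say relapse only. The operative reading is that death is censored. What stands is that two programmers could differ, which is itself a reason to amend the wording.

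**The endpoint's role is modest.** SAP 7.3.7 makes duration of CR supportive, without formal testing. This stands in full: no error rate and no co-primary test is touched.

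**Deaths are counted elsewhere.** A reader might infer that the plan conceals toxic deaths. It does not. OS counts every death, and Protocol 4.2 gives this as its purpose: "The trial includes a co-primary endpoint of OS to confirm no decrement in survival from severe toxicity". PFS counts death, and the SAP also summarises 30- and 60-day mortality and causes of death. The gap is narrower: none of these isolates deaths in remission by arm.

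**The size cannot be anchored in the documents.** A reader might take the 15.7% 60-day mortality in the Phase 2 treatment-naïve cohort as a guide. It covers all 51 subjects, not responders. In this trial the first scheduled on-treatment marrow falls on Day 1 of Cycle 3, about Day 57 (2 × 28 + 1), so most deaths by Day 60 would precede any documentable CR. Nor does anything in the documents show more deaths in CR with guadecitabine; the contrast in step 5 is assumed, and is shown in both directions for that reason.

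**Redefining the endpoint would change the protocol.** This is right. The relapse-only definition is the protocol's own, and adding analyses beside it is enough.

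**Conclusion.** The point holds for this endpoint. Followed as written, the plan censors a competing event, and the reported duration of CR exceeds the time responders spend alive in CR whenever anyone dies in remission; if nobody does, the bias is zero. The inflation factor 1/(1 − s) rests on constant hazards, and the values of s are illustrative. An imbalance between arms in deaths in CR would not appear in the planned medians.

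The conclusions on CR rate and OS are unaffected. What suffers is the description of how durable the remissions are. The matter should be corrected before analysis, but it is no threat to the trial's primary inference.

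**What to change.** In SAP 7.3.10, state how death without documented relapse is handled, and reconcile that sentence with the death item in 7.3.6. Keep the protocol's relapse-only definition and add:

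- (a) time from first CR to relapse or death from any cause, by Kaplan-Meier, for each arm;
- (b) cumulative incidence of relapse with death in CR as a competing event, for each arm;
- (c) the number of deaths in CR by arm.

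Base statements about durability on (a) and (b), and label the relapse-only estimate as such.

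The cost is a few sentences of SAP text and a little programming. Response, progression and survival status are already collected until death (Protocol 9.5.6), so no new data and no change of protocol endpoint are needed. The one downside for the sponsor is that the duration under (a) will be shorter than the relapse-only figure.

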by a blinded independent central response reviewer, based on assessment by a blinded independent central pathologist. Refer to Section 11.6 of the study protocol. The specific process used for handling test samples and reports will be described separately.

Peripheral blood (PB) will be assessed at baseline and on Day 1 of each cycle for response status evaluation. Bone marrow (BM) aspirate/biopsy will be performed at screening and then at the end of Cycles 2, 4, and 6 unless PB shows persistence of leukemic blasts that excludes the possibility of a marrow response. After Cycle 6 BM assessment, BM aspirate/biopsy will be repeated every 3 months for the first year on study and then every 6 months thereafter until PB or BM assessment shows disease progression or relapse. Response evaluation will be based on BM blinded assessment and the most concomitant PB counts. After blinded BM response is confirmed, assessment of normal count recovery will be done based initially on the most concomitant PB and in later cycles on PB counts from Day 1 of each cycle to avoid transient treatment-induced normal count suppression.

Figure 1 below summarizes the study design.

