## 4.0 SAMPLE SIZE

By trial design, the overall (2-sided) alpha level of 0.05 is split between the co-primary endpoints of CR (0.04) and OS (0.01). A formal interim analysis will be performed only for OS using a group sequential boundary preserving an overall (2-sided) 0.01 alpha level. The sample size calculation for the primary analysis of CR is based on testing at the 0.04 nominal alpha level. If statistical significance is achieved for CR, hierarchically, the final analysis of OS will be conducted to preserve an overall 2-sided 0.05 alpha level, accounting for alpha spent at the interim analysis of OS, as described in Section 11.6.7 and Section 11.9 of the study protocol (see Section 7.3.7 and 7.6). The sample size calculation for OS will be shown for the setting of a 2-sided 0.05 alpha level.

Assuming a CR rate of approximately 0.20 ([Kantarjian et al 2012](#); [Fenaux et al 2010](#); [Burnett et al 2007](#)) for subjects treated in the TC group (all TC therapies combined) and assuming an increase in CR rate to 0.30 or higher can be achieved by treating subjects with guadecitabine,

800 subjects (400 per treatment group) will provide approximately 89% power to detect the overall difference of 0.10 when using a 2-sided Cochran Mantel-Haenszel test having 2-sided alpha level of 0.04. For the purpose of this sample size calculation, the constant CR rates of 0.20 and 0.30 for the TC and guadecitabine groups, respectively, are assumed for each stratum.

For survival, an analysis at 670 death events will provide 90% power to detect a HR of approximately 0.78 (a difference in median survival of 7 months in the TC group versus 9 months in the guadecitabine group), when using a 2-sided stratified log-rank test at an 0.05 alpha level. Accrual is expected to be uniform over a 21 month enrollment period, with an additional follow-up of 12 months. Hence, the assessment of survival needs approximately the same sample size of 800 subjects. Primary response and survival analyses will be performed after 670 death events have occurred. For the purpose of this sample size calculation, a constant HR of approximately 0.78 was assumed for all strata defined by the stratification factors.

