**Figure 2: The Hierarchical Test Order and Related Alpha Values**

The overall alpha error rate is controlled at the 0.05 level by following the above testing sequence and procedures.

Other secondary efficacy endpoints (number of transfusions, health-related QOL, and duration of CR) will be used as supportive evidence of the beneficial treatment effect, without formal hypothesis testing. Point estimates and 95% CIs will be obtained for the effect of treatment on these endpoints.

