### 7.3.9 EQ-5D-5L Descriptive System Total Score and the EQ VAS

The EQ-5D-5L descriptive system scores and the EQ VAS will be collected for each subject for a minimum 6 months unless the subject dies or withdraws consent prior. The calculation for EQ-5D-5L index value will be performed according to EuroQol group's EQ-5D-5L User Guide (<http://www.euroqol.org/about-eq-5d.html>).

As suggested in the EQ-5D-5L User Guide (<http://www.euroqol.org/about-eq-5d.html>), the EQ-5D-5L descriptive scores and their dichotomized levels (No problems, Problems) within each EQ-5D dimension (mobility, self-care, usual activity, pain/discomfort, anxiety/depression), during the first 6 months, will be summarized by time (ie, visit/treatment cycle) descriptively, using counts and proportions. The EQ-5D-5L index value and VAS and their respective changes from baseline during the first 6 months will be summarized by time (ie, visit/treatment cycle) using means, standard deviations, medians and quartiles.

In addition, the changes from baseline (post baseline value - baseline value) of EQ-5D-5L index value, and separately EQ VAS, will be analyzed using a mixed model approach for repeated measures. This model will include the following terms as fixed effects: baseline value, treatment, time, and treatment-by-time interaction. The unstructured covariance matrix will be used to account for the within subject correlation and allow for different variances at different measurement times. The difference of the least squares means between the two treatment groups at each time (ie, visit/treatment cycle) and its corresponding 95% CI will be provided.

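### SAP 7.3.10 summarises the all-subject duration-of-CR analysis only by medians and quartiles, five of six of which are expected to be 0 days, and names no between-arm estimate

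*SAP*

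**What the plan says.** SAP 7.3.10 defines duration of CR as running from the first CR to relapse, with relapse defined by leukemic blasts in blood or marrow. It plans two Kaplan-Meier analyses. One covers subjects who reached CR. The other covers the whole Efficacy Analysis Set: "a separate Kaplan-Meier analysis including all subjects will be conducted with a 0-day event duration assigned to subjects who did not achieve a CR". For each, the listed output is the same: "The median and quartiles of duration of complete response, as well as their respective 95% CIs will be provided". SAP 7.0 has summary tables presented by treatment group, so the all-subject analysis yields three quantiles in each of two arms.

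SAP 7.3.7, in the text after Figure 2, places duration of CR among the secondary endpoints that support the main result without formal testing, and adds: "Point estimates and 95% CIs will be obtained for the effect of treatment on these endpoints". Section 7.3.10 does not say what that estimate is.

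Protocol 11.6.10 describes the same all-subject analysis and has the two groups compared by a log-rank test. The SAP does not carry that test over.

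**The concern.** The all-subject analysis is the only duration analysis that keeps the randomised groups intact; the responder analysis compares subsets selected by outcome. If most of its tabulated quantiles are zero by construction, the table conveys almost nothing about duration.

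The treatment-effect estimate promised in 7.3.7 is also undefined. SAP 7.3.9 shows how it could have been done, since it names its contrast for quality of life: "The difference of the least squares means between the two treatment groups at each time", with a 95% CI. In an open-label trial, a contrast that is left open could be chosen after the data have been seen.

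**Working it through.** **Inputs.** SAP 4.0 gives 400 per group, two-sided alpha 0.04 for CR, and "the constant CR rates of 0.20 and 0.30 for the TC and guadecitabine groups, respectively, are assumed for each stratum". It also gives the follow-up: "Accrual is expected to be uniform over a 21 month enrollment period, with an additional follow-up of 12 months". Marrow timing is in SAP 3.1: "Bone marrow (BM) aspirate/biopsy will be performed at screening and then at the end of Cycles 2, 4, and 6". The documents give no planning value for CR duration, so the durations in step 4 are assumptions.

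**1. The plan's own figure.** Power for 0.20 vs 0.30:
- Pooled SE = √(2 × 0.25 × 0.75/400) = 0.0306.
- Unpooled SE = √((0.20 × 0.80 + 0.30 × 0.70)/400) = 0.0304.
- z = (0.10 − 2.054 × 0.0306)/0.0304 = 1.22, so power is 0.889. The stated 89% is reproduced.

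**2. Expected quantiles.** Each subject without CR is an event at day 0, so just after day 0 the curve equals the CR rate p. The q-th quantile is 0 days when 1 − p ≥ q.

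| Arm | 1 − p | Lower quartile | Median | Upper quartile |
|---|---|---|---|---|
| TC | 0.80 | 0 | 0 | 0 |
| Guadecitabine | 0.70 | 0 | 0 | above 0 |

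Five of six are 0. The pattern is the same at the phase 2 CR rates of 33% (Protocol 2.1) and 37% (SAP 1.3), and at the comparator rates of 8% to 20% quoted in SAP 1.3.

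**3. How likely this is in the data.** An upper quartile is 0 when an arm has at most 100 CRs out of 400 (exact binomial).
- TC, p = 0.20: 0.9938. Guadecitabine, p = 0.30: 0.0155.
- Exactly five zero: 0.9938 × (1 − 0.0155) = 0.978.
- All six zero: 0.9938 × 0.0155 = 0.015.
- Four zero: 0.0062 × 0.9845 = 0.006.
- Counting fewer than 100 CRs instead changes 0.978 to 0.980.

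The pattern turns on which side of 25% each rate falls. At p = 0.25 an arm's upper quartile is 0 in 53% of trials. At 0.30 vs 0.40 both upper quartiles are almost always above 0.

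The interval adds little for TC. With a log(−log) interval (assumed here; the SAP names it for OS), the 95% CI for the TC curve just after day 0 is 0.162 to 0.241. This lies wholly below 0.25, so the CI for the TC upper quartile also collapses to 0.

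**4. What a between-arm contrast would show.** Take restricted mean time in CR over 12 months from first CR, with 0 for subjects without CR. For exponential time in CR with median m and λ = ln 2/m, the arm mean is p × (1 − e^(−12λ))/λ. For m = 6 this is 0.20 × 6.49 = 1.30 and 0.30 × 6.49 = 1.95 months.

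| Assumed median, TC / guadecitabine (months) | TC | Guadecitabine | Difference | SE | 95% CI |
|---|---|---|---|---|---|
| 4 / 4 | 1.01 | 1.51 | 0.50 | 0.207 | 0.10 to 0.91 |
| 6 / 6 | 1.30 | 1.95 | 0.65 | 0.249 | 0.16 to 1.14 |
| 8 / 8 | 1.49 | 2.24 | 0.75 | 0.273 | 0.21 to 1.28 |
| 12 / 12 | 1.73 | 2.60 | 0.87 | 0.301 | 0.28 to 1.46 |
| 8 / 4 | 1.49 | 1.51 | 0.02 | 0.238 | −0.44 to 0.49 |

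With equal durations the ratio is 0.30/0.20 = 1.5, the CR-rate ratio. In the last row a halved duration is offset by the higher CR rate, and only the responder table would reveal it.

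**5. Is a 12-month horizon supported?** Potential follow-up after first CR is 33 − u − t months, with entry time u uniform on 0 to 21 and t the months to first CR. The share with less than 12 months is t/21.
- For t of 2, 4 and 6 it is 9.5%, 19.0% and 28.6%. Averaged over t uniform on 2 to 6, about 81% have the full 12 months.
- Later responders do worse: at t of 8 to 10 the shortfall is 38% to 48%. Protocol 7.1.2 reports such cases. Of 51 phase 2 subjects, 2 responded and another 2 improved to CR after more than six cycles.

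**The case against.** The strongest case against the point has four parts.

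- **The curves already carry the information.** They show the CR proportion and its decay for all randomised subjects, and the responder analysis describes durability directly. This stands. A reader might infer that the SAP leaves duration of CR without informative output; the documents do not support that. The weakness lies in the all-subject table and the missing estimate.
- **A comparison was pre-specified.** Protocol 11.6.10 has the log-rank test, and dropping it agrees with the SAP's no-testing rule. A reader might infer that no comparison was ever planned, or that the contrast is bound to be picked after the fact. Neither follows; the choice is open, so it could be made late. But a log-rank test supplies no point estimate or CI, so it does not meet the promise in 7.3.7.
- **A hazard ratio is the obvious default.** The text does not say so, and here it is fragile. About 320 + 280 = 600 of 800 subjects are tied at day 0. In 200 simulated trials (assumed 6-month median in both arms, first CR at 2 to 6 months, the plan's accrual and follow-up), the average unstratified hazard ratio was 0.90 with Breslow ties and 0.82 with Efron ties.
- **The restricted mean shares the fault.** It too blends response and durability, and it is one choice among several. This is true and must be stated beside it. Still, it gives a number with a CI where the quantiles give zeros.

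The gap is also not unique to this endpoint: SAP 7.3.8 on transfusions names no between-arm estimate either.

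**Conclusion.** The point holds and is minor. On the SAP's own CR rates, the listed all-subject output is nearly degenerate (five of six quantiles at 0 days, probability 0.978), and the estimate promised in 7.3.7 has no counterpart in 7.3.10. The count rests on the TC rate being at most 25% and the guadecitabine rate lying between 25% and 50%. It does not depend on any assumed CR duration.

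Nothing here touches type I error, sample size or the co-primary conclusions. The endpoint is supportive and untested, and OS is measured directly. The month figures in the working only illustrate the proposed contrast and are conditional on assumed durations.

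**What to change.** Keep the Kaplan-Meier curves, the listed quantiles and the responder analysis. Add to SAP 7.3.10, as the estimate required by 7.3.7, one supportive contrast in the Efficacy Analysis Set: the difference (guadecitabine minus TC), with 95% CI from Greenwood-type variances, in restricted mean time in CR over a fixed horizon. A suitable horizon is 360 days from first CR, which is 12 of the SAP's 30-day months. Subjects without CR count as 0 days, and subjects still in CR are censored at the last assessment without relapse.

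State the event rule. Under the SAP definition only relapse ends duration of CR, so deaths in CR are censored. If death in CR is to end the time counted, label the measure time in CR (relapse or death), say that it differs from the first-CR-to-relapse duration, and show a responder-only summary under the same rule beside the planned one.

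The cost is a few sentences and modest programming, with no new data and no change to the planned duration endpoint. There are three downsides. The measure combines response rate and durability, so it must be read with the responder table. It depends on the horizon. And full 12-month follow-up at about 81% of responders holds only if first CR falls at 2 to 6 months.
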